3.2 Secondary Endpoints

- 3.2.1 The ORR (CR + PR) at 10 weeks will assessed based on RECIST v1.1 criteria.
- 3.2.2 PFS rate at approximately 6 months (i.e. 27 weeks) is defined as the time from day 1 of treatment until disease progression or death status measured 6 months after initiating study treatment. Progression events will be defined per RECIST v1.1 criteria.
- 3.2.3 The toxicity will be assessed based on the NCI CTCAE v 5.0 criteria. For example, the incidence of AEs that occur in subjects enroll who receive at least one dose of therapy.

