5.0 TREATMENT PLAN

5.1 Schema

Eligible subjects must have histologically confirmed AJCC stage III/IV melanoma of any subtype and sufficient, archived metastatic tumor tissue to confirm absence

of TIL/TAL in representative H&E-stained tumor tissues. Subjects are eligible even if they have received any prior PD-1/PD-L1 pathway inhibitors or any other systemic treatments, including immunotherapies, on condition that they have not received HDACi for their melanoma. They must have recovered from any side effects associated with prior anticancer treatments. Patients will be 'primed' with entinostat, 5mg PO qwk, for 3 weeks. In the end of cycle 1, beginning of cycle 2 (day 22±2 days), immediately before concurrent entinostat-pembrolizumab treatment, they will undergo a mandatory melanoma biopsy after which they will receive up to 4 infusions of standard of care pembrolizumab along with weekly administration of entinostat. Restaging radiographic studies will be performed on week 10 and then every 6 weeks until week 27. Peripheral blood will be collected at baseline; in the end of cycle 1, beginning of cycle 2 (day 22±2 days), immediately before concurrent entinostat-pembrolizumab treatment; on week 10 after 3 infusions (cycles) of pembrolizumab; and at the end of treatment, either at disease progression or week 27, or if intolerable toxicity occurs that requires permanent discontinuation of pembrolizumab and/or entinostat. Subjects will be considered to have completed all trial requirements if:

- (a) Their disease has progressed by RECIST v1.1 criteria within less than 10 weeks from the first dose of entinostat,
- (b) They develop toxicity related to pembrolizumab or entinostat, but still complete sample collection (peripheral blood and tumor tissue) and tumor assessments by at least week 3,
- (c) Complete the entire 27 weeks of combination therapy and study-related assessments without experiencing disease progression by RECIST v1.1 criteria or clinical grounds. Those subjects experiencing clinical benefit after 27 weeks may continue pembrolizumab therapy per standard of care.

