6.3.6 Disease Assessment

This following test should be performed for assessment of melanoma disease.

6.3.6.1 Computed tomography (CT) of the whole body i.e., neck (if applicable), chest, abdomen, pelvis with IV contrast (or abdominal/pelvis MRI if allergy to IV contrast)

Baseline (screening) disease assessment should be obtained within 21 days of initiating study treatment. During the study, scans will be repeated as outlined in the Time and Events table in section 7.1 (i.e., at the end of week 10[D1 of cycle 4 or Study day 64/Wk10], end of week 15 [D1 of cycle 6 i.e., Study day 106/Wk16], end of week 21 [D1 of cycle 8 or Study day 148/Wk22], and end of week 27). Scans obtained during study treatment may be performed within ± 7 days of the scheduled study visit.

6.3.6.2 *Magnetic Resonance Imaging (MRI) of the brain*

MRI of the brain must be obtained at baseline (screening) and at end of treatment (i.e., at time of disease progression or at week 27); on any other visit **only if clinically indicated**, as per standard of care. If brain MRI is not feasible, patient can have a CT scan with IV contrast.

6.3.7 **Pre-Screening Pathology Assessment Period (pre-screening only)**

Given the limited 21-day screening period, and the requirement for absent TIL/TAL in melanoma tissues, archival metastatic tissue (locoregional, distant metastatic) can be requested and assessed before study enrollment (pre-screening). There is not an official pre-screening period given that [name], study's pathologist, is UNC's sole melanoma pathologist and routinely signs off his pathology reports, either from outside consultation slides or from in-house cases, along with a report about the presence of absence of tumor-infiltrating/-associated lymphocytes. If not available already, representative tumor sections from archived tumor blocks will be stained with H&E and will be assessed by [name], study pathologist, for assessment of quality using these criteria: (1) the tumor surface area must be at least 1cm² (which can be from a combination of metastatic blocks if necessary), (2) no more than 20% of necrosis, (3) the ratio of viable tumor cells to tumor-associated stroma should be at least 60/40, and (4) if TILs are present based on H&E stained sections, they must be $\leq 1\%$ of the total number of cells in the specimen; the amount of tissue should be ≥ 1 cm².

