7.0 EVALUATIONS AND ASSESSMENTS

7.1 Time and Events Table

Assessments ¹	Pre-screening	Screening ¹ D-21→-0	Study Treatment ³							End of Tx ⁴ ±7d	Long-term follow up ⁴
			D1 Wk1	D22 Wk4	D43 Wk7	D64 Wk10	D85 Wk13	D106 Wk16	D127, D148, D169 Wks19, 22, 25		
			D1 Cycle 1	D1 Cycle 2	D1 Cycle 3	D1 Cycle 4	D1 Cycle 5	D1 Cycle 6	D1 Cycles 7, 8, 9		
Informed Consent ²	X	X									
History, PE		X	X	X	X	X	X	X	X	X	X
Serum/Urine Pregnancy Test		X	X								
ECOG PS		X	X	X	X	X	X	X	X	X	
Concomitant Meds		X	X	X	X	X	X	X	X	X	
Hematology		X	X	X	X	X	X	X	X	X	
Serum Chemistry		X	X	X	X	X	X	X	X	X	
Endocrine tests		X				X		X	X ⁵	X	
Coagulation tests ⁵		X									
Urinalysis ⁶		X	X								
12-lead ECG		X		X		X		X	X	X	
Toxicity Assessment		X	X	X	X	X	X	X	X	X	
Brain MRI		X								X	
Whole body CT		X				X		X	X ⁸	X	
Patient pill diary (entinostat)			X	X	X	X	X	X	X	X	
Entinostat ⁷			X	X	X	X	X	X	X ⁸		
Pembrolizumab ⁷				X	X	X	X	X	X ⁸	X ⁹	
Blood for isolation of PBMCs			X	X		X				X	
Archival tissue assessment ¹⁰	X										
Fresh Tumor Biopsy				X ¹¹							
FoundationOne®		X									

(Note: Week 1 includes days 1-7; week 2 includes days 8-14; week 3 includes days 15-21, etc.)

Key to Footnotes

1. All screening assessments should be obtained within 21 days before initiating study treatment, unless specified below:
 - a. Screening labs obtained within 72 hours of D1 of study treatment do not need to be repeated on D1/cycle 1 visit.
 - b. The serum pregnancy test should be obtained during screening and a urine pregnancy test should be obtained within 72 hours before starting entinostat treatment on D1/cycle 1.
2. Informed consent at pre-screening visit in order to access archival tissue or perform fresh tissue biopsy if archival tissue is unavailable or insufficient, to confirm unresectable stage III or distant metastatic disease. Main consent is to be signed at the screening visit.
3. Study Treatment assessments:
 - a. All study treatment visits should be performed within (± 1) day for the first two weeks of study therapy.
 - b. For the cycle 1/day 2 visit (i.e., Study Day 22) visit the window is ± 2 days,
 - c. Then ± 3 days for assessments scheduled on D1 of cycles 3 and 4 and then ± 7 days for assessments scheduled on D1 of all subsequent cycles.
4.
 - a. Refer to section 7.5.1 for guidance on end of study treatment requirements for this study.
 - b. Refer to section 7.5.2 for guidance on long-term follow up requirements for this study.

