7.5 Post Treatment Follow-Up Assessments

7.5.1 End of Study Treatment Visit (Week 28, or earlier if disease progression, intolerable toxicity, patient withdraw) within + 7 days of stopping study treatment

1. Clinical evaluation: focused history and physical exam,
2. ECOG performance status,
3. 12-lead ECG
4. Laboratory studies:
 - Hematology
 - Serum Chemistries
 - Endocrine panel: include fT4/TSH only
5. Disease assessment (chest, abdomen and pelvis; neck if applicable),
6. Collect peripheral blood for isolation of PBMCs and plasma (approximately 50 mL)
7. Brain MRI (if applicable),
8. Concomitant medication review,
9. Toxicity Assessment.

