9.1.1 Definitions

Evaluable patients are those who complete all activities by at least day 22, namely: (a) they have received at least one and up to 4 entinostat weekly doses on day 1 and day 8, 15 and 22 (b) they have received the first pembrolizumab infusion on day 22 (± 2 days), and (c) they have completed day 22 (± 2 days) mandatory tumor biopsy. The rationale for this is to answer the primary translational endpoint regarding entinostat-alone immunomodulatory effects in peripheral blood and tumor tissue with sufficient power.

- SAE are events that meet FDA's definition as defined in [section 8.1.4](#) of the protocol irrespective of attribution to study drug(s). Subjects who receive at least one dose of entinostat are evaluable for safety.

- ORR by RECIST 1.1 criteria is the sum of complete response and partial response.

- PFS is measured from the date of enrollment on study to the date of documented progression. The rate of patients who are progression-free will be specifically calculated at 27-weeks (approximately 6 months) from study entry.

- OS is measured from the date of enrollment on study to the recorded date of death. The rate of patients who are alive at 27-week (approximately 6 months) will be specifically calculated for the study.

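### The 27-week PFS rate is read at a day that the final scan can miss, so late-detected progressions count as progression-free and bias the rate upward

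*Combined protocol and SAP*

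**What the plan says.** **The rate.** Section 9.1.1 states: "PFS is measured from the date of enrollment on study to the date of documented progression". It then fixes the landmark: "The rate of patients who are progression-free will be specifically calculated at 27-weeks (approximately 6 months) from study entry". Section 3.2.2 describes the same endpoint differently, as "defined as the time from day 1 of treatment until disease progression or death status measured 6 months after initiating study treatment". Section 9.3 names Kaplan-Meier as the estimator. The rate is secondary objective 2.2.2.

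**The scans.** Section 6.3.6.1 schedules study days 64, 106 and 148, then a last scan; its wording for the final two is "end of week 21 [D1 of cycle 8 or Study day 148/Wk22], and end of week 27". It adds: "Scans obtained during study treatment may be performed within ± 7 days of the scheduled study visit". Section 5.1 says: "Restaging radiographic studies will be performed on week 10 and then every 6 weeks until week 27", and section 9.1 repeats the 6-week step. Section 7.5.1 attaches the final disease assessment to the "End of Study Treatment Visit (Week 28, or earlier if disease progression" and asks for that visit within 7 days of stopping study treatment.

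**Week numbering.** The note to the table in 7.1 reads: "Week 1 includes days 1-7; week 2 includes days 8-14; week 3 includes days 15-21, etc". Week 27 is therefore days 183 to 189, and week 28 is days 190 to 196.

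**The concern.** A Kaplan-Meier curve dated by documented progression drops on the day of the scan that shows it. If that scan comes after the landmark, the patient is still at risk and event-free at 27 weeks, even if the disease progressed weeks before. No scan is scheduled between day 148 and the final one, so whenever the final scan is late the 27-week rate shows status at week 22 instead.

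The plan does not assign a late final scan to week 27, extend the landmark over the scan window, or treat progression as interval-censored. The error can only run upward. In a single-arm trial this rate serves for description and for comparison with outside figures, and an upward error affects both.

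**Working it through.** The documents give no target, power or precision for 27-week PFS, so there is no stated figure to reproduce.

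**1. Landmark.** 27 × 7 = 189 days. Counted from day 1 of treatment this is study day 190. Counted from enrollment, as in 9.1.1, it falls earlier by the gap between enrollment and day 1. That gap is not stated; I take 0 to 21 days as possible, bounded by the 21-day screening period.

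**2. Where the final scan can fall.** Only a scan strictly after the landmark causes this loss; an event on the landmark day itself is counted. Share of possible scan days strictly after it:

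| Reading of the final scan | Gap 0 days | Gap 3 days | Gap 7 days |
|---|---|---|---|
| End of week 27, day 189 ± 7 (6.3.6.1) | 6/15 = 40% | 9/15 = 60% | 13/15 = 87% |
| Six weeks after day 148, day 190 ± 7 (5.1, 9.1) | 7/15 = 47% | 10/15 = 67% | 14/15 = 93% |
| Week 28 visit, days 190–196 (7.5.1) | 6/7 = 86% | 7/7 = 100% | 7/7 = 100% |
| Within 7 days of the last entinostat dose on day 183 (7.5.1 with 5.2.1) | 0/8 = 0% | 3/8 = 38% | 7/8 = 88% |

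**3. Size.** Assumptions: constant hazard; progression found only at scheduled scans; no losses or censoring before the landmark. The anchor is the 46.4% 6-month PFS that section 1.5.2 cites for pembrolizumab every 3 weeks. It comes from a different population and serves only as illustration.

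- S(t) = 0.464^(t/182.6), with t in days.
- S(189) = 0.452, the true 27-week rate.
- S(147) = 0.539, status at the day-148 scan.
- Value read = average over possible scan days of S(scan time) if the scan is on or before the landmark, and S(147) if after.

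Counted from day 1:

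- Every final scan late: 0.539 − 0.452 = 0.087, or +9 points.
- Days 190–196: (0.452 + 6 × 0.539)/7 = 0.527, or +7 to 8 points.
- Day 190 ± 7: eight scan days on or before the landmark average 0.458, so (8 × 0.458 + 7 × 0.539)/15 = 0.496, or about +4 points.
- Day 189 ± 7: nine scan days on or before the landmark average 0.459, so (9 × 0.459 + 6 × 0.539)/15 = 0.491, or about +4 points.
- Days 183–190: average 0.458, or under +1 point.

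**4. Other assumed true rates.** If every final scan is late, the rate read is the true rate raised to the power 147/189: 10% reads 16.7%, 20% reads 28.6%, 30% reads 39.2%. The excess is 7 to 9 points, or at most 0.92 of 10 patients.

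**5. Does the fix remove it?** With day 190 ± 7 and the curve read at study day 197 (196 days from day 1), every final scan in the window counts. The average of S over 182 to 196 days is 0.452, which matches the true 27-week rate under these assumptions.

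**The case against.** The strongest reply is that the effect depends on choosing among conflicting passages.

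- **How often the scan is late.** A reader might infer that the final scan usually misses the landmark and that the rate therefore largely ignores it. The documents do not support this in general. Counted from day 1, as in 3.2.2, only 40% to 47% of a window of 7 days either side falls strictly after the landmark. None does if stopping treatment in 7.5.1 means the last dose on day 183.
- **What end of week means.** It is tempting to fix the last scan at day 190 because 6.3.6.1 equates the end of week 15 with day 106 and the end of week 21 with day 148. The same sentence equates the end of week 10 with day 64, which is the first day of that week. The usage is inconsistent and settles nothing.
- **Detection between scans.** Patients are examined on day 169, skin lesions can be measured with calipers, and 7.5.1 moves the final assessment forward on progression. Some progressions will be dated in time, so the figures are at the upper end.
- **Intent.** The plan could mean status at the nominal final assessment. Section 3.2.2 speaks of status at about 6 months, and 9.3 does not name a reading day.
- **Importance.** The endpoint is secondary, with no target or decision rule.

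All of this limits the size and the frequency. None of it supplies a rule for a final scan that falls after the landmark. Section 9.1.1 as written counts such a patient as progression-free, and the intended reading would have to be written in.

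**Conclusion.** The concern holds in this form: the final scan can fall after the 27-week landmark, and progressions first documented there are counted as progression-free, so the rate is biased upward. The excess is about 0 to 9 points: about 4 with scans spread evenly over 7 days either side counted from day 1, and up to 9 only if every final scan is late and progression is found only by scan. In ten patients that is at most about one. These sizes rest on a constant hazard, the borrowed 46.4% figure and an unstated gap between enrollment and day 1. Dose delays, allowed up to 15 days in cycles 7 to 9 (5.3), could push cycle-linked scans later; I have not added them to the range.

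The primary endpoint and its decision rule are unaffected. The point is still worth correcting before analysis, because it biases a named secondary objective in one direction and costs only wording to remove.

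**What to change.** 1. In 3.2.2, 9.1.1 and 9.3, use one time origin, day 1 of treatment, and one event definition: RECIST progression or death.
2. Read the Kaplan-Meier rate at one fixed day, the close of the protocol window for the final scheduled scan (for example study day 197 for day 190 + 7). Progression or death up to that day then counts as an event for the 27-week rate.
3. State the censoring rule with it. A patient whose final scan inside the window shows no progression, and who has no event by that day, should stay at risk until it. Censoring such patients at the scan date would leave the end of the curve resting on the few scanned last. Sections 5.9 and 7.5.2 already collect later progression in patients who complete 27 weeks without it.
4. Report final scans obtained after that day in a sensitivity analysis that assigns their progressions to the final scheduled assessment. One Kaplan-Meier reading day cannot move to fit each delayed scan.
5. Reconcile the week 27 and week 28 label and the window for this scan across 5.1, 6.3.6.1, 7.1, 7.5.1 and 9.1, including what stopping study treatment means in 7.5.1.

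The cost is wording. No scans or patients are added, and the reported rate may be slightly less favourable.

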9.1.2 Correlative Studies

This study is unusual for “traditional” phase II cancer trials in that the primary endpoint is actually a translational correlative and not a clinical efficacy endpoint. Correlative analysis relies on the collection of peripheral blood and tumor tissue on which power size calculations are based (see Section 9.2, Sample Size and Accrual). Specific data analysis plans for the correlative studies are presented in Section 9.3.

9.2 Sample Size, Accrual and Duration of Accrual

Our goal is to enroll at least 10 evaluable patients. The immune-mediated mechanism of action of entinostat alone (primary translational endpoint) will be evaluated on representative H&E-stained tissue sections from tumor tissues collected at baseline and on day 22 by standard pathology analysis. This analysis will be conducted by [name], study pathologist. Density of TIL/TALs in these H&E-stained sections will be scored as a 0, 1+ (non-brisk), 2+ (brisk) ordinal variable¹⁵¹. By definition, upon enrollment if TILs are present based on H&E stained sections, they must be $\leq 1\%$ of the total number of cells in the specimen. A non-inflamed melanoma may have been ‘successfully’ converted to an inflamed melanoma following 21 days of entinostat ‘priming’ if the histopathologic analysis of day 22 melanoma biopsies shows any (i.e. brisk or non-brisk) evidence of TIL/TAL. In other words, we will capture the incidence of conversion as a dichotomous variable, present (i.e. brisk or non-brisk) or absent. Twenty-one days of entinostat ‘priming’ would be considered to have an immunomodulatory effect if at least 3 out of 10 evaluable patients show conversion of their melanomas from ‘non-inflamed’ to ‘inflamed’. This test has a type I error rate of 0.04 if the true rate is 0.08 and power of 83% if the true rate is 0.4.

The secondary endpoint is antitumor response by RECIST 1.1. Given that one of the determinants of response to single-agent PD-1 inhibitors is pre-existing TIL/TAL²⁹, we postulate that patients with metastatic melanoma and zero TIL/TAL will have nearly zero response rate. With 10 patients the exact 95% confidence interval for response rate is (0, 0.31) if 0 responses are observed out of 10 patients, and (0, 0.45) if 1 response is observed out of 10 patients.

Assuming that 20% of patients will not be evaluable due to screen failure, toxicity or rapid disease progression, and another 30% of enrolled patients will not have interpretable tumor biopsies on day 22 due to necrosis, stromal contamination or overall low quality, the total number of enrolled patients should be set to 14.

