1.0 BACKGROUND AND RATIONALE

1.1 Study Synopsis

This is an exploratory (n=10-12 evaluable patients), open-label, single-arm, phase II study in patients with ‘non-inflamed’ unresectable regional or distant metastatic melanomas irrespective of prior treatment with PD-1/PD-L1 pathway inhibitors. The primary endpoint is to assess the incidence of histopathologic conversion of non-inflamed melanomas from patients with metastatic melanoma to ‘inflamed’ melanoma following single-agent entinostat “priming” (entinostat monotherapy). More specifically, patients with metastatic melanomas that have no evidence of tumor-infiltrating or tumor-associated lymphocytes (TIL/TAL), based on standard hematoxylin and eosin (H&E) staining of representative tumor sections (non-inflamed melanomas) will receive weekly entinostat for 3 weeks in cycle 1 (entinostat monotherapy; 5mg PO, qwk on D1, D8, D15 of cycle 1; cycle length = 21 days). Mandatory tumor tissue biopsies will be performed in the end of cycle 1, beginning of cycle 2 (day 22±2 days), immediately before treatment with concurrent entinostat (once weekly × 3) and pembrolizumab (200 mg q3wks) in cycles 2-9 (see section 5.2.1 drug dosing schema). Correlative studies will be performed at baseline and in the end of cycle 1, beginning of cycle 2 (day 22±2 days) to assess whether: (a) 3 weeks of entinostat monotherapy converts TIL/TAL-absent melanomas to TIL/TAL-present by histopathologic (H&E stain) analysis, (b) 3 weeks of single-agent entinostat induces changes in gene expression profiling by assessing distinct signatures as defined by RNA-sequencing signatures (RNA-seq; ‘immune-high’, innate anti-PD-1 resistance [IPRES], and epigenetic¹⁻³), (c) 3 weeks of single-agent entinostat induces changes in histone-accessible DNA by performing formaldehyde-assisted isolation of regulatory elements (FAIRE)⁴, (d) conversion of non-inflamed to inflamed melanomas by single-agent entinostat and/or antitumor response to the entinostat-pembrolizumab combination is associated with a baseline signature that consists of distinct somatic mutation gene profile, global histone modification profile in melanoma tissue or peripheral blood mononuclear cells (PBMC), and/or abundance of entinostat targets in melanoma cells (HDAC 1, 2, 3, and 11). Up to 12 evaluable patients will be treated with entinostat plus pembrolizumab for up to 27 weeks (approximately 6 months) based on clinical benefit. Patients who continue to have clinical benefit at 27 weeks may continue therapy with pembrolizumab or any other PD-1/PD-L1 inhibitor, as per standard of care.

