4.1 Inclusion Criteria

- 4.1.1 Age \geq 18 years at the time of consent.
- 4.1.2 Subject has provided informed consent and HIPAA prior to initiation of any study-specific activities/procedures.
- 4.1.3 ECOG Performance Status of ≤ 2 .
- 4.1.4 Histologically confirmed metastatic (regional or distant) melanoma of any subtype (cutaneous, mucosal, ocular).
- 4.1.5 AJCC stage unresectable III or stage IV disease that is measurable by RECIST v1.1 criteria.
- 4.1.6 Must agree to undergo one on-treatment tumor biopsy on day 22 (± 2 days) of the study. Subjects for whom fresh samples cannot be safely provided (e.g., inaccessible tumor for biopsy) will not be eligible for study participation.
- 4.1.7 Must have available archival tissue and subjects must have consented to allow collection of archived tumor blocks from previous surgeries confirming or treating unresectable stage III or distant metastatic disease. If more than one archived tumor block is available, only one block is required to be analyzed for the presence of TIL/TALS. Archived tumor tissues must fulfill the following criteria based on two representative H&E-stained tissue sections: (1) the tumor surface area must be at least 1cm^2 (which can be from a combination of metastatic blocks if necessary), (2) no more than 20% of necrosis, (3) the ratio of viable tumor cells to tumor-associated stroma should be at least 60/40, and (4) if TILs are present based on H&E stained

sections, they must be $\leq 1\%$ of the total number of cells in the specimen; the amount of tissue should be ≥ 1 cm².

[name], study pathologist, must sign off on the eligibility of archived tumor blocks before study enrollment. If archival tissue is unavailable or insufficient, fresh biopsy should be performed to confirm unresectable stage III or distant metastatic disease.

4.1.8 Previous treatment with immune checkpoint inhibitors and chemotherapies is allowed on condition that the last treatment is at least 28 days prior to first dose of entinostat. Previous treatment with targeted therapies (e.g. MAPK inhibitors) is allowed on condition that the last treatment was administered at least 15 days prior to first dose of entinostat).

4.1.9 Demonstrate adequate organ function as defined in the table below; all screening labs to be obtained within 21 days prior to entinostat treatment.

System	Laboratory Value
Hematological*	

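### The study pathologist both certifies baseline eligibility and scores the day-22 endpoint biopsy with no masked read specified; a coded, masked re-read should define the primary endpoint

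*Combined protocol and SAP*

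**What the plan says.** **Who reads.** For the H&E assessment of baseline and day-22 sections, Section 9.2 states "This analysis will be conducted by" the study pathologist. Criterion 4.1.7 says the study pathologist "must sign off on the eligibility of archived tumor blocks before study enrollment", and one condition is that any TILs make up no more than 1% of cells. Section 6.3.7 repeats that condition and describes the study's pathologist as the only melanoma pathologist at the institution.

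**What counts.** TIL/TAL density is graded by eye as 0, 1+ (non-brisk) or 2+ (brisk) and then reduced to present or absent. A tumor is converted if the day-22 biopsy shows "any (i.e. brisk or non-brisk) evidence of TIL/TAL".

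**Decision rule.** Entinostat priming is declared immunomodulatory if "at least 3 out of 10 evaluable patients show conversion of their melanomas". Section 9.2 adds: "This test has a type I error rate of 0.04 if the true rate is 0.08", with "power of 83% if the true rate is 0.4".

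**How the read is done.** Section 9.2 describes it only as a standard pathology analysis. The visible text mentions no masking to time point, coded slides, second reader or adjudication. The synopsis (Section 1.1) describes the trial as open-label and single-arm.

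**The concern.** The endpoint is a visual call at the lowest step of a three-level scale, made by the role that has already passed the patient as non-inflamed. In a single-arm trial of a drug expected to bring lymphocytes into the tumor, a reader aware of the time point may lean toward seeing a sparse infiltrate at day 22. There is no control biopsy to show how often an untreated tumor would be called positive.

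Selection adds to this. Patients enter only if the baseline was called absent or at most 1%, so a baseline that was under-called is enrolled, and a correct day-22 read then scores as a conversion. The thresholds also differ: eligibility tolerates TILs up to 1% of cells, while conversion needs any TIL/TAL, so an unchanged tumor with a sparse infiltrate could be scored as converted.

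With about 10 evaluable patients, a few such calls could decide whether the trial reports an immunomodulatory effect.

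**Working it through.** **Inputs from Section 9.2.** n = 10 evaluable; success if the number of conversions X is at least 3; null rate 0.08; alternative rate 0.40. The documents give no reader error rate, so the error rates below are assumptions.

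**1. Reproduce the plan's figures** (exact binomial).
- Type I error = 1 − [0.92^10 + 10(0.08)(0.92^9) + 45(0.08²)(0.92^8)] = 1 − [0.4344 + 0.3777 + 0.1478] = 0.040.
- Power = 1 − [0.6^10 + 10(0.4)(0.6^9) + 45(0.4²)(0.6^8)] = 1 − [0.0060 + 0.0403 + 0.1209] = 0.83.

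Both agree with the plan.

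**2. When one call decides.** A false positive changes the result only at X = 2, and a missed conversion only at X = 3.
- At a rate of 0.08, P(X = 2) = 0.148 and P(X = 3) = 0.034.
- At a rate of 0.40, P(X = 2) = 0.121 and P(X = 3) = 0.215.
- Upper bound for one extra positive: if a count of 2 always became 3, false success would be 0.040 + 0.148 = 0.188.
- Upper bound for one lost conversion: if a count of 3 always became 2, power would be 0.833 − 0.215 = 0.618.

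**3. Assumed false upgrades.** Let f be the chance that an unconverted tumor is called converted. The apparent null rate is p = 0.08 + 0.92f, and the type I error is P(X ≥ 3) at that p.

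| f | p | Type I error |
|---|---|---|
| 0 | 0.080 | 0.040 |
| 2% | 0.0984 | 0.067 |
| 5% | 0.126 | 0.122 |
| 10% | 0.172 | 0.240 |

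**4. Assumed missed conversions.** Let s be the sensitivity of the day-22 read. The apparent alternative rate is 0.40s.

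| s | 0.40s | Power |
|---|---|---|
| 100% | 0.40 | 0.83 |
| 95% | 0.38 | 0.80 |
| 90% | 0.36 | 0.76 |
| 80% | 0.32 | 0.67 |

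**What step 3 does not show.** f is total false-upgrade error. A masked read by the same person keeps ordinary reading error and removes only the part due to expectation. The formula also treats 0.08 as free of misreads. The plan does not say what 0.08 represents; if it already allows for apparent conversion without a drug effect, adding f on top counts some error twice.

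**The case against.** A reader might infer that the pathologist scores the day-22 slide knowing which slide it is. The documents do not say so. They are silent on masking, parts of Section 9.3 are redacted, and the laboratory manual cited in Section 7.6 is not available. Awareness is plausible, because the baseline is read before enrollment and the day-22 tissue is a fresh biopsy, but it remains an inference.

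A reader might also infer that the two slides are never compared. Section 9.2 describes one analysis covering both time points, and Sections 2.1 and 3.1 define the endpoint on both, so a paired read is compatible with the text.

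Nor does every day-22 error add a conversion. Overlooking a sparse infiltrate in a tumor that did convert loses one, as step 4 shows. And sensitivity to one patient belongs to any 3-of-10 rule, whoever reads the slides.

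On proportion: the synopsis calls the study exploratory and plans 10 to 12 evaluable patients. CD8 immunofluorescence (Section 1.7.2.3.1) and computer image analysis (Section 9.3.4) on both time points offer less subjective corroboration. They are exploratory or secondary, however, and do not feed the decision rule.

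These points limit the claim and its size. What stands is that one role performs both assessments and that Section 9.2, where the endpoint read is defined, specifies no masking.

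**Conclusion.** The concern holds in limited form. The plan gives the eligibility sign-off and the subjective endpoint score to the same study pathologist and specifies no masking to time point, in a design where expectation would favor conversion. That the two tasks fall to one person rests on the role title and Section 6.3.7, since names are removed.

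The stated operating characteristics are arithmetically correct, but they assume that reading error does not alter the conversion rates entered. Even an assumed 2% false-upgrade rate moves the type I error from 0.040 to 0.067, and 10% moves it to 0.240. These figures show how sensitive the rule is to total error; they are neither an estimate of this reader's error nor the gain from masking. One call changes the decision only at a count of exactly 2 or 3.

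This is an inexpensive improvement that should be made. It is not evidence that the endpoint read will be biased.

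**What to change.** Amend Section 9.2 as follows.

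- At study end the same pathologist re-reads all baseline and day-22 H&E slides, coded by someone else, in random order, masked to patient, time point and response, on the 0/1+/2+ scale. This read defines the primary endpoint; the unmasked read serves eligibility only.
- A conversion is counted only when the masked day-22 grade is higher than the same patient's masked baseline grade.
- Every evaluable patient stays in the denominator. A baseline re-read as 1+ with an unchanged day-22 grade is a non-conversion, not an exclusion.

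The second and third points also deal with the mismatch between the 1% eligibility limit and the any-TIL conversion threshold. The masked baseline grades will show how often a certified baseline is called positive on re-reading, which the plan currently cannot tell.

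**Cost.** One extra session plus slide coding: at one slide per time point, 2 × 10 = 20 slides for 10 evaluable patients, up to 2 × 14 = 28 for the 14 enrolled. No extra biopsy, pathologist or patients are needed. A patient whose baseline is re-read as 1+ must reach 2+ to convert, so power would fall somewhat if such patients are common; the documents do not allow this to be quantified. Masking will be imperfect where archival resections and day-22 cores look different.
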